9.5. Planned Analyses

The primary analysis will occur when all participants have completed the 28 days post-Dose 2 visit or have discontinued earlier. These analyses will include immunogenicity data on quantification of antibody binding to full-length HA and HA stem protein and safety data up to the 28 days post-dose 2 visit. At the time of the primary analysis, the study will be unblinded for sponsor and external partnerships personnel who are involved in the data analysis and decision making. Participants and study-site personnel will remain blinded to the study vaccine allocation until the end of the study.

An additional analysis will occur when all participants have completed the 6-month post-Dose 2 visit or discontinued earlier. These analyses will include additional safety data up to the 6 months post-Dose 2 visit and immunogenicity data required per the sponsor's assessment. This analysis may allow to evaluate persistence of immune responses.

No study modifications are planned as a result of primary or additional analyses. The exact scope of each analysis will be defined based on the availability of immunogenicity data and findings from previous analyses. Additional interim analyses may be performed during the study for the purpose of informing future vaccine development-related decisions in a timely manner, or upon health authority request. If required, these unplanned interim analyses may replace or be combined with planned analyses, depending on the timing.

The final analysis will occur when the last participant has completed the final visit of the schedule of assessment (Day 365±30 days) or discontinued earlier. Final analyses will allow for determination of the durability of the immune response and analyze any additional safety and immunological data collected after the additional analysis.

The SAP will describe the planned analyses in greater detail.

Based on safety and immunogenicity results, the sponsor's Vaccine Development Committee will decide which regimen will be taken forward. Additional factors such as data from other assays, literature, epidemiology data, manufacturability, and ease of administration will be taken into account to select the regimen for the next clinical study.

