## **Breadth Score**

Three types of breadth scores will be calculated based on breadth panel assays, listed in [Table 5](#) using Maximum Diversity Weighting method ([Z. He, Y. Fong, Stat Med. 2019](#)) (R package: “mdw”):

- Narrow H1 score (H1 strains as identified in [Table 5](#)):
  - o Although the vaccine backbone mini-HA ELISA does assess an H1 HA, this ELISA may also measure neo-epitope immune responses against design elements of the protein, which could potentially result in an inflated mini-HA ELISA response in FLZ1001. Therefore, the vaccine backbone mini-HA ELISA (A/California/07/2009) results will be excluded from the H1 Breadth Score.
- Broad Group 1 score (Group 1 strains as identified in [Table 5](#)):
  - o The vaccine backbone mini-HA ELISA (A/California/07/2009) results will be excluded from the Group 1 Breadth Score (same reason as for Narrow H1 score).
  - o The H7 and B ELISAs will also be excluded from the Group 1 Breadth Score as these are Group 2 and Flu B antigens, respectively, and do not represent Group 1 HAs.
- Group 1 score excluding H1 (Group 1 strains as identified in [Table 5](#)):
  - o All H1 (including the mini-HA ELISA) results will be excluded from the Group 1 score excluding H1.
  - o The H7 and B ELISAs will also be excluded from the Group 1 score excluding H1 as these are Group 2 and Flu B antigens, respectively, and do not represent Group 1 HAs.

The Breadth score will be calculated for each participant only when all ELISAs used in the calculation are non-missing. For each ELISA included in the breadth score calculation, values below LLOQ will be imputed to LLOQ/2, and values above the upper limit of quantification (ULOQ) will be imputed with the ULOQ. Calculation of the breadth score is done separately at each analysis.

The following results will be calculated: N, geometric mean§ and corresponding 95% CI, interquartile range, min, max of the actual values, and fold increases from baseline will be tabulated and graphically presented. §calculate the mean and corresponding 95%CI of  $\log_{10}$  transformed values, back-transform this mean [i.e.,  $10^{\text{mean}}$ ] and CI [i.e.,  $10^{\text{CI}}$ ].

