### 5.7.1.6.2. Humoral assays

Descriptive statistics and graphs on humoral immunogenicity data listed in [Table 4](#) (where available) will be done similarly as described in section [5.7.1.5.1.](#) for the COV3005 Broad SF-SC cohort (H5 ELISA, mini-HA ELISA, VNA, Human Fc $\gamma$ RIIIa reporter assay, breadth ELISAs including three breadth scores, coverage score, and HAI assay) and for the SF-SC cohort.

For H5 ELISA, mini-HA ELISA, VNA, Human Fc $\gamma$ RIIIa reporter assay, and three breadth scores, geometric mean ratios (GMR)  $\ddagger$  between active groups (FLZ1001 vs. SF-SC cohort), with corresponding 95% CIs will be estimated via an analysis of variance (ANOVA), using log-transformed 28 days post-dose 1 immune parameter response as dependent variable and study group as independent variable. As a sensitivity analysis, the ANOVA may also be performed adjusting for the respective baseline titers, by including log-transformed baseline titer as an additional covariate.  $\ddagger$ by back-transform LSmean and corresponding 95%CI from ANOVA [i.e.,  $10^{LSmean}$ ] and CI [i.e.,  $10^{CI}$ ].

In addition, GMR plots over time, combining the regimens in one graph (without individual participant dots) will also be created.

For the breadth coverage, least square mean differences between active groups (FLZ1001 vs. SF-SC cohort), with corresponding 95% CIs will be estimated via an analysis of variance (ANOVA), using 28 days post-dose 1 breadth coverage as dependent variable and study group as independent variable. As a sensitivity analysis, the ANOVA may also be performed adjusting for the respective baseline value, by including baseline breadth coverage as an additional covariate.

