## **5.8. Interim Analyses**

There are no plans for interim analyses with an intent to stop the study early or to adapt the design or planned number of patients. However, there will be planned analyses at pre-specified timepoints as described in the study protocol (please refer to the CTP section 9.5 Planned Analyses).

DPS will identify which outputs will be produced for each analysis.

Based on safety and immunogenicity results, the sponsor's Vaccine Development Committee will decide which regimen will be taken forward. Additional factors such as data from other studies\* or other assays, literature, epidemiology data, manufacturability, and ease of administration will be considered to select the regimen for the next clinical study.

\*Additional analyses might be performed on immunogenicity data up to 29 days post-dose 1 from the external control group (COV3005 study). Two cohorts will be presented:

1. independent analysis will be performed on the Broad SF-SC cohort of COV3005 (200 subjects' cohort), followed by
2. selection of the SF-SC (matching ZLF1001 population) and analysis of the SF-SC cohort.

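### The breadth-score weights are not fixed across analyses, and nothing requires FLZ1001 and the seasonal-vaccine reference cohort to share them

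*SAP*

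**What the plan says.** SAP 5.7.1.5.1 (Breadth Score) defines a narrow H1 score, a broad Group 1 score and a Group 1 score excluding H1, each calculated "using Maximum Diversity Weighting method" through a named R package. Only complete cases contribute: "The Breadth score will be calculated for each participant only when all ELISAs used in the calculation are non-missing". The timing rule follows: "Calculation of the breadth score is done separately at each analysis". The section does not say which participants, visits or cohorts determine the weights, or whether the weights are carried forward.

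Elsewhere in the SAP, an analysis means a planned data cut. Section 5.8 says "DPS will identify which outputs will be produced for each analysis" and refers to Protocol 9.5, which plans three:
- "The primary analysis will occur when all participants have completed the 28 days post-Dose 2 visit or have discontinued earlier";
- "An additional analysis will occur when all participants have completed the 6-month post-Dose 2 visit or discontinued earlier";
- a final analysis after the Day 365 visit.

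For the external control, SAP 5.7.1.6.2 applies the same descriptive work to the Broad SF-SC cohort, covering "breadth ELISAs including three breadth scores, coverage score, and HAI assay", and to SF-SC. It then estimates geometric mean ratios (GMRs) of the three breadth scores, FLZ1001 versus SF-SC, at 28 days post-dose 1. SAP 5.8 adds that an "independent analysis will be performed on the Broad SF-SC cohort of COV3005", followed by selection and analysis of SF-SC.

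The other breadth summary, breadth coverage, is treated differently: its distance matrix is printed as SAP Table 6.

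**The concern.** A weighted score is a defined quantity only once its weights are. The SAP's rule leaves three things open: whether a sample keeps its score from one cut to the next, whether Day 1 and post-dose values share weights (fold increases in the score are tabulated), and whether both sides of the FLZ1001 versus SF-SC ratio use the same weights.

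The third matters most. SF-SC is a subset of the 200 people in Broad SF-SC. Under the stated rule, one serum from one person could carry one score in the Broad SF-SC analysis and another in the SF-SC analysis. If either cohort-specific score were then set against FLZ1001, part of the GMR would reflect the weights. The planned ANOVA has study group, and optionally baseline, as its only terms, so its confidence interval would not show that part. Running the samples side by side, as SAP 5.7.1.6 provides, aligns the assays but not the weights.

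Immunogenicity results feed the choice of regimen (Protocol 9.5, SAP 5.8), and the SF-SC comparison is the only one with a seasonal vaccine.

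**Working it through.** The plan states no weight, precision or power for the breadth score, so there is no figure of its own to reproduce. The SDs below come from Protocol Table 5. That table does reproduce with a two-sample t-test (n = 22 per group, two-sided 0.05): for a 2-fold difference at SD 0.301, the noncentrality is 0.301 / (0.301 × √(2/22)) = 3.32 and the power is 90.0%, as printed.

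**Step 1: effect of a weight shift.** Assume log10(score) = Σ wⱼ log10(xⱼ) with Σ wⱼ = 1. The SAP does not state the scale. Moving weight Δw between two antigens whose readings differ by a ratio r multiplies the score by r^Δw. For an assumed r = 10:
- Δw = 0.05: 10^0.05 = 1.12
- Δw = 0.10: 10^0.10 = 1.26
- Δw = 0.20: 10^0.20 = 1.58

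**Step 2: between data cuts.** The primary cut follows the Day 85 visit, so all Day 29 visits are past.
- If the weights use only Day 1 or only Day 29 data, the Day 29 score changes only through late results, changes to the per-protocol set, or changes in assay status. SAP 5.7.1.3 foresees the last, and 4 of the 9 non-extended broad Group 1 ELISAs in SAP Table 5 are only partially qualified.
- If the weights pool all visits available at each cut, a simulation (SD 0.301, assumed post-dose rises, 300 runs) gave a Day 29 geometric mean at the final cut of 0.93 to 1.01 times its primary-cut value (5–95%). The Day 29 active/placebo GMR moved by a factor of 0.997 to 1.018.

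**Step 3: between cohorts, identical true titres (true GMR = 1).**
- From the documents: the nine non-extended broad Group 1 antigens; distances from SAP Table 6; 22 per regimen (Protocol 9.2); 76 in SF-SC (stated in the SAP for the extended panel); SDs 0.301 and 0.421.
- Assumed: 150 FLZ1001 participants contributing weights; baseline log10 means of 2.0 to 3.3; correlation exp(−k × distance), with k = 0.5 in both cohorts (same) or 0.5 and 1.5 (different).
- Weights: minimise w′Rw with w ≥ 0 and Σw = 1, where R is the correlation matrix. This is a stand-in for data-driven diversity weights, not the package itself. 300 runs per row.

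| Correlations | SD | GMR, common weights: median (5–95%) | GMR, separate weights: median (5–95%) | Separate ÷ common, 5–95% |
|---|---|---|---|---|
| Same | 0.301 | 0.99 (0.80–1.27) | 0.97 (0.66–1.51) | 0.74–1.36 |
| Same | 0.421 | 1.02 (0.71–1.37) | 1.01 (0.59–1.66) | 0.70–1.34 |
| Different | 0.301 | 0.99 (0.79–1.28) | 0.92 (0.64–1.39) | 0.69–1.27 |
| Different | 0.421 | 1.00 (0.73–1.34) | 0.92 (0.62–1.42) | 0.69–1.22 |

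A median of 0.25 of the total weight differed between the cohorts. Across the four rows, separate weights changed the GMR by a factor of 0.69 to 1.36. The size depends on the assumed spread of antigen means (3.3 − 2.0 = 1.3 log10, about 20-fold); with a smaller spread it would be smaller.

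**Step 4: when the antigen profiles differ.** With an assumed H1-leaning response in SF-SC and SD 0.301, the median GMR was 1.20 under pooled weights, 1.28 under separate weights, and 1.38 when either cohort's weights were applied to both. Even a common set must therefore be named in advance.

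**The case against.** Several objections have force.
- The SAP sentence concerns calculating the score. It does not mention weights or re-estimation. That the weights are data-driven is inferred from the named method, and from the oddity of a separate calculation per analysis if they were preset.
- No contrast of breadth scores between data cuts is planned, and SAP Table 4 assigns durability to the H5 ELISA.
- The independent analysis is of Broad SF-SC, whereas the GMR comparator is SF-SC. That GMR comes from one ANOVA containing both cohorts, which can naturally be read as one analysis with one score calculation. The data presentation specifications and the COV3005 study plan may settle this, but are not available here.
- Every panel ELISA is presented individually, and breadth coverage, with its printed matrix, is also compared with SF-SC. A reader could see whether a result hinges on weighting.
- Breadth is exploratory and no immunogenicity hypothesis is tested. Protocol 2.1 ties regimen selection to the secondary endpoints.

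These points limit the size and the certainty, but not the gap: no text requires one weight set, and the score cannot be reproduced from the SAP.

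A reader might infer more: that the Day 29 score is a different quantity at each cut, that FLZ1001 and SF-SC are given separate weights, or that unblinded post-vaccination data shape the endpoint. The documents support none of these as fact. Each is only permitted by what is left unsaid, and Step 2 suggests that the first would be small.

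**Conclusion.** The point holds as a matter of definition. The SAP has the score calculated separately at each analysis, fixes no weights, and does not require FLZ1001 and SF-SC to share them.

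For Day 29 across data cuts, the likely effect is small: under 2% on the active/placebo GMR in the simulation. For FLZ1001 versus SF-SC, it would matter if either reference cohort is scored in its own analysis. The illustrative factor of 0.69 to 1.36 is not negligible beside the 1.5- to 3-fold differences in Protocol Table 5. It appeared mainly as added spread, with median GMRs of 0.92 to 1.01. It rests on a stand-in for the method, assumed correlations and assumed antigen means; the actual size cannot be derived from the documents.

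Because the endpoint is exploratory and descriptive, this is a worthwhile, inexpensive improvement and does not threaten a primary or secondary conclusion.

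**What to change.** In SAP 5.7.1.5.1, replace the sentence on separate calculation with a rule that:
- estimates the weights once for each score, including the extended versions, on a named set that pools FLZ1001 and SF-SC samples and is blinded to group;
- prints the weights in the SAP or the report, as Table 6 does for the distances;
- applies them unchanged to all visits, all data cuts and both cohorts.

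Pooled Day 1 samples are one option, since they precede vaccination. First check the share of values below LLOQ for each antigen: these enter as the constant LLOQ/2, and an antigen with many of them would carry little usable information for weighting. Add an unweighted mean of log10 values as a sensitivity analysis.

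Cost: a short SAP rule, one table, and six weight sets to document (three scores, standard and extended). The extended sets rest on the selected subset only. The weights will not adapt to later data, which is the price of a score that means the same thing wherever it appears.

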### **Extended Breadth Score**

The analysis of extended breadth score will be performed on a subset of participants from the PPI analysis set who have samples for analysis at both Day 1 and Day 29.

A random selection of about 75 participants in total from three FLZ1001 study groups and 76 participants from SF-SC cohort from VAC31518COV3005 study (see section 5.7.1.6.1) will be made. For FLZ1001, all participants meeting criteria from the INFLUENZA G1 mHA CCI - INFLUENZA G1 mHA CCI group will be included in the subset. A random sample of 30 participants from the pooled group of INFLUENZA G1 mHA CCI - INFLUENZA G1 mHA CCI and INFLUENZA G1 mHA CCI - placebo groups and from the pooled group of INFLUENZA G1 mHA CCI Al(OH)3 - INFLUENZA G1 mHA CCI Al(OH)3 and INFLUENZA G1 mHA CCI Al(OH)3 - placebo groups will be made respectively. Selecting 30 subjects will allow for a total of 25 subjects to be included in the subset from each of those two groups, where subjects with vials with low volume are excluded.

The same three types of breadth scores (Narrow H1 score, Broad Group 1 score, and Group 1 score excluding H1) will be calculated based on the extended breadth panel assays (as identified in Table 5) using Maximum Diversity Weighting method. The ELISAs that were included in the original breadth scores are also included in the extended breadth scores for selected subjects. The extended breadth scores will include additional ELISAs as detailed below:

- Narrow H1 score (H1 strains as identified in Table 5):
  - o The same ELISAs that are included in the Narrow H1 score.
  - o In addition, the mini-HA ELISA (A/New Caledonia/20/1999) is included.
- Broad Group 1 score (Group 1 strains as identified in Table 5):
  - o The same ELISAs that are included in the Broad Group 1 score.
  - o In addition, the following ELISAs are included: mini-HA (A/New Caledonia/20/1999); H5 (A/Cambodia/NPH230032/2023); H2 (A/avian/Japan/KU-d3c/2020); and H9 (A/Cambodia/21020301/2021).
- Group 1 score excluding H1 (Group 1 strains as identified in Table 5):
  - o The same ELISAs that are included in the Group 1 score excluding H1.
  - o In addition, the following ELISAs are included: H5 (A/Cambodia/NPH230032/2023); H2 (A/avian/Japan/KU-d3c/2020); and H9 (A/Cambodia/21020301/2021)

Analysis will be done in a similar way as described above for the Breadth score.

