8.1. Immunogenicity Assessments

Immunogenicity assessments may include, but are not limited to, the immunogenicity assays (as available and applicable) summarized in [Table 3](#). Timings of blood draws are specified in Section [1.3](#), Schedule of Activities.

Immunogenicity assessments supporting the secondary endpoint were chosen to quantify the magnitude of the pre-existing influenza-specific immunity and vaccine-induced antibody responses that are thought to contribute to the protective capacity of HA stem-based vaccination approaches. Antibodies targeting the stem domain of the influenza HA molecule will be quantified by ELISA using full-length HA or stem-only antigens that are expected to sensitively and specifically detect responses targeting the conserved stem domain of the molecule.

Immunogenicity assessments supporting the exploratory endpoint were chosen to further quantify the magnitude and characterize pre-existing influenza-specific immunity and vaccine-induced immune responses. This characterization entails a deeper investigation of the breadth and functionality of the antibody response, the set-up of assays and characterization of mucosal targeting of the immune response, and characterization of cellular and molecular effects of vaccination.

Although this study is not designed to support the identification or validation of surrogates of protection against clinically manifest influenza infection, immunological assessments supporting the secondary and exploratory endpoints will be evaluated for their utility as potential surrogates of protection, to be applied to and further characterized in follow-up studies, such as challenge studies or Phase 2b proof-of-concept studies.

Blood for humoral immune responses will be drawn from all participants. Influenza immunity in study participants will be determined on baseline (Day 1) and post-vaccination blood samples as described in Section [1.3](#), Schedule of Activities. Both assay variability and pre-existing immunity will be taken into consideration in the immunogenicity assessments.

PaxGene tubes and proteome stabilization samples will be collected according to Section [1.3](#), Schedule of Activities. PaxGene samples will allow the performance of whole blood transcript profiling.

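### The extended Narrow H1 and Broad Group 1 breadth scores add a second mini-HA ELISA, and the SAP does not say why its neo-epitope concern about the first does not apply

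*SAP*

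**What the plan says.** SAP 5.7.1.5.1, under Breadth Score, explains why one mini-HA ELISA is left out of the Narrow H1 score. It "may also measure neo-epitope immune responses against design elements of the protein, which could potentially result in an inflated mini-HA ELISA response in FLZ1001". The consequence is that "the vaccine backbone mini-HA ELISA (A/California/07/2009) results will be excluded from the H1 Breadth Score", and the Broad Group 1 score follows for the same reason. SAP Table 5 lists that construct as mH1, UFV180702, reported separately and in no breadth score.

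Under Extended Breadth Score, the extended Narrow H1 score keeps its earlier components and gains one: "In addition, the mini-HA ELISA (A/New Caledonia/20/1999) is included". The extended Broad Group 1 score gains the same ELISA together with newer H5, H2 and H9 antigens. SAP Table 5 shows it as mH1*, UFV190137, marked Y for both scores. It has no Y for the Group 1 score excluding H1 or for Breadth Coverage, and it does not appear in the distance matrix (SAP Table 6).

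The extended scores are computed in about 75 FLZ1001 participants and 76 SF-SC participants, who received standard-dose seasonal vaccine in COV3005. SAP 5.7.1.6.2 plans geometric mean ratios of FLZ1001 to SF-SC, with 95% CIs, for the individual assays and three breadth scores.

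**The concern.** The stated reason for the exclusion is about the engineered protein, not the strain: full-length H1 from the same California virus (UFV181009) stays in both scores. A reader would expect that reason to be considered for any other mini-HA construct. The SAP does not consider it for the New Caledonia one. Nor does that ELISA bring in a new strain, because full-length New Caledonia H1 (UFV181089) is already a component.

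Any error of this kind would run one way. FLZ1001 vaccinees received a mini-HA protein; SF-SC participants did not. The three FLZ1001 groups named for the extended subset are all active groups, so SF-SC is the only control there. Antibody to engineered parts of the vaccine could then be counted as breadth in the candidate's favour. SAP 5.8 lists data from other studies, with a footnote to COV3005, among the factors for choosing the regimen to take forward. A distorted ratio could therefore carry weight even though no hypothesis is tested.

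**Working it through.** The plan gives no figure to reproduce on this point. The check is a count of components followed by a conditional calculation.

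**Step 1. Count the ELISAs marked Y in SAP Table 5, without and with the starred (extended-only) rows.**

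| Summary | Original | Extended | Mini-HA in the extended version? |
|---|---|---|---|
| Narrow H1 | 4 | 5 | Yes, the only addition |
| Broad Group 1 | 9 | 13 | Yes, 1 of 4 additions |
| Group 1 excluding H1 | 5 | 8 | No |
| Breadth Coverage | 9 | 12 | No |

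The extended Narrow H1 score therefore differs in content from the original only through the mini-HA ELISA.

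**Step 2. Effect on a ratio against SF-SC.** Assume that the score is a weighted mean of log ELISA values, that the New Caledonia mini-HA has weight w, and that it reads k-fold too high after vaccination in FLZ1001 only. The log ratio then shifts by w × log k, so the geometric mean ratio is multiplied by k^w. Neither k nor w is in the documents.

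Equal weights:

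| k (assumed) | Narrow H1, w = 1/5 | Broad Group 1, w = 1/13 |
|---|---|---|
| 1 | 1.00 | 1.00 |
| 2 | 1.15 | 1.05 |
| 4 | 1.32 | 1.11 |
| 10 | 1.58 | 1.19 |

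**Step 3. Unequal weights.** The SAP uses Maximum Diversity Weighting, which may give more weight to an assay less correlated with the rest. As a stand-in, take the weights that minimise the variance of the weighted mean of standardised logs. With p full-length assays correlated r with each other and m with the mini-HA, let v = (1 + (p − 1)r)/p. Then w = (v − m)/(1 + v − 2m), set to 0 if negative.

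- Narrow H1, p = 4, r = 0.8, m = 0.6: v = 0.85 and w = 0.25/0.65 = 0.385. With k = 4 the factor is 4^0.385 = 1.71.
- Broad Group 1, p = 12, same r and m: v = 0.817 and w = 0.217/0.617 = 0.351. With k = 4 the factor is 4^0.351 = 1.63.
- With m = 0.8 the weights return to 0.20 and 0.077, the equal-weight values. With m = 0.85 both are 0.
- For Narrow H1 over r = 0.7 to 0.9 and m = 0.3 to 0.7, w runs from 0.20 to 0.47.

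The larger factors depend entirely on the assumed correlations.

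**Step 4. Without the New Caledonia mini-HA.** Extended Narrow H1 has 4 ELISAs and extended Broad Group 1 has 12. The factor from this assay is 1.00 for any k.

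**The case against.** A reader might infer that the SAP rejects mini-HA ELISAs in general as inflated, and that the extended comparison is therefore biased. The documents do not support that. The exclusion names only the vaccine-backbone construct, and it speaks of possible inflation, not observed inflation. UFV190137 is a separate construct, and nothing in the documents says that it shares the vaccine's design elements. The common mini-HA label makes sharing plausible but does not show it. This objection stands, and it makes the point conditional.

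The extended scores are also not named in the SF-SC comparison in SAP 5.7.1.6.2. That is correct. However, the Extended Breadth Score text calls for analysis similar to the Breadth score, and it draws the subset jointly with 76 SF-SC participants and no placebo group. A ratio against SF-SC is the natural use.

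There are safeguards. The original scores, both versions of the Group 1 score excluding H1 and both coverage analyses contain no mini-HA. Each panel ELISA is presented individually, breadth is exploratory, and a large gap between original and extended scores would be visible. These limit the harm but do not supply the missing justification. The absence of this ELISA from Extended Breadth Coverage is weak evidence of inconsistency, because that method works from an HA sequence alignment and may reasonably use different inputs.

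A reader might also want the mini-HA ELISA taken out of the SF-SC ratios ("For H5 ELISA, mini-HA ELISA, VNA"). That goes too far. It is a core assay supporting the secondary endpoint, and Protocol 8.1 chose "stem-only antigens that are expected to sensitively and specifically detect responses targeting the conserved stem domain of the molecule". Reporting its ratio with the SAP's own caveat attached is sufficient.

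**Conclusion.** The point holds as an unexplained inconsistency with a possible one-directional effect, confined to two of the three extended scores. The SAP recognises a risk for one mini-HA construct, adds another without addressing that risk, and plans no version without it. If UFV190137 shares design elements with the vaccine antigen, ratios against SF-SC on the extended Narrow H1 and Broad Group 1 scores are too favourable to the candidate. For an assumed k = 4 and equal weights the factors are 1.32 and 1.11. Factors of about 1.6 to 1.7 need both that k and assumed correlations that favour the mini-HA. If no elements are shared, k = 1 and this bias is absent. The documents do not settle which case applies, so the conclusion that the comparison is in fact biased is not available from them.

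**What to change.** In the Extended Breadth Score text and SAP Table 5:

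- For comparison with SF-SC, calculate the extended Broad Group 1 score without the New Caledonia mini-HA (12 ELISAs, keeping the added H5, H2 and H9 antigens). For Narrow H1 in the subset, use the four full-length H1 ELISAs, with weights estimated in that analysis as the SAP already provides.
- Show the 13- and 5-component versions as sensitivity analyses. If the SAP documents that UFV190137 shares no design elements with the vaccine antigen, the present definitions can stand.
- Keep reporting the New Caledonia mini-HA ELISA individually, as planned for every breadth-panel assay.
- In SAP 5.7.1.6.2, keep the mini-HA ELISA ratio and carry the neo-epitope caveat with it.

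The cost is SAP wording, a table edit and a small amount of extra analysis, with no new samples or assays. The drawback is that the main Narrow H1 score in the subset gains no new antigen.
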